4.2.7. Withdrawals, Dropouts, Lost to Follow-up

Subjects who withdraw from the study will not be replaced.

4.2.8. Missing, Unused, and Spurious Data

In general, there will be no substitutions made to accommodate missing data points, unless otherwise specified (see sections 4.6, 4.8.2 and 4.8.8). All data recorded on the electronic Case Report Form (eCRF) will be included in data listings that will accompany the Clinical Study Report.

4.2.9. Visit Windows

For summaries by timepoint, the time windows given in Table 3 will be applied to allocate measurements to analysis visit. This will be done for laboratory parameters, vital signs, ECG, NYHA Classification, KCCQ-12, and EQ-5D.

In general, in case multiple measurements are collected in the same window, the value closest to the target day as specified in Table 3 will be used for analysis. If there are 2 values with the same time before and after the target day, the later value will be used for analysis. If there are 2 continuous values on the same date then the average of the values will be used. For categorical variables, if there are more than 1 value on the same date then the worst case will be chosen (e.g. for EQ-5D).

Table 3 Analysis Assessment Windows

Parameter	Visit Label	Analysis Assessment Window (Efficacy/Safety)
Laboratory parameters, Vital signs, ECG, NYHA Classification	Baseline	≤1 day
	Week 6	Day 43 [2; 64] days
	Week 12	Day 85 [65; 107] days
	Week 24	Day 169 [108; 253] days
	Week 52	Day 365 [254; 408] days
EQ-5D	Baseline	≤1 day
	Week 6	Day 43 [2; 85] days
	Week 24	Day 169 [86; 253] days
	Week 52	Day 365 [254; 408] days
KCCQ-12	Screening	N/A
	Baseline	≤1 day
	Week 2	Day 14 [2; 20] days
	Week 4	Day 28 [21; 34] days
	Week 6	Day 43 [35; 64] days
	Week 12	Day 85 [65; 107] days
	Week 24	Day 169 [108; 211] days
	Week 36	Day 253 [212; 295] days
	Week 52	Day 365 [296; 408] days

4.2.10. Handling of Missing and Partial Dates

Imputation of missing and partial event dates, such as hospitalisation, AE and concomitant medication start and stop dates, is described in sections 4.6, 4.8.2 and 4.8.8.

4.2.11. Definition of First Study Day (SD1)

First study day (SD1) is defined as the date of first administration of IV FCM or placebo.

For efficacy assessments, study day will be computed from the randomisation into the study.

4.2.12. Definition of Baseline

Baseline is defined as the last non-missing assessment prior to or at SD1. More specifically, baseline is defined as the last record or measure collected prior to the first dose of investigational medicinal product (IMP).

If an assessment is collected on SD1 and either time of assessment or time of first dose is missing, then such assessment is considered as prior to the first dose. The exception for this rule are medications and AEs, which will be considered as concomitant or treatment-emergent, respectively.

4.2.13. End of Study (Last Visit)

End of study is defined as the date of the Week 52 visit for subjects completing the study, or the date of the early study termination visit for other subjects.

In cases where the subject dies, if the last visit is reported after death then death date will be used as last day in study.

4.2.14. Time on Study

Time on study for safety purposes is calculated for each subject from SD1 to the last known date:

$$\text{Time on study (days)} = (\text{Last Known Date} - \text{SD1}) + 1.$$

Time on study for efficacy purposes is calculated for each subject from randomisation date to the last known date:

$$\text{Time on study (days)} = (\text{Last Known Date} - \text{Randomisation Date}) + 1.$$

If last known date is outside of visit window for Week 52 visit (i.e. after study day 375), time on study will be 375 days for such subjects and only events up to this day will be considered.

4.2.15. Time on Study Drug

Time on study is calculated for each subject from SD1 to the date of last study drug injection:

$$\text{Time on study drug (days)} = (\text{Last Study Drug injection date} - \text{SD1}) + 1$$

4.2.16. Last Available Value

The last available value is defined as the last available value across visits, including unscheduled measurements.

4.2.17. Time since Initial Diagnosis

Time since initial diagnosis is calculated in years for each subject with known documented HF prior to index hospitalisation as the time since the diagnosis was made as of the informed consent date.

Time since diagnosis (years) = (Informed consent date – date of diagnosis + 1)/365.25

In case the diagnosis date is completely missing, the time since diagnosis will be missing. Otherwise, if the year and month are not missing, then the day will be set to 1. If the day and month are both missing, they will be set to 01JAN.

4.2.18. Subject-Years of Time on Study

Subject-years of time on study is the sum of all subjects' times on study (overall or by treatment groups) expressed in years.

Subject-years of time on study = [Sum_i(time on study in days)] / 365.25, i=1 to n, where n is the number of subjects.

Note: for 30-days analysis, the time on study will be up to 30 days after randomisation.

4.2.19. Conversion Factors

The following conversion factors will be used to convert days into months or years, or vice versa:

- 1 week = 7 days,
- 1 month = 30.4375 days, and
- 1 year = 365.25 days.

The following conversion factors will be used for height and weight:

- 1 cm = 0.39370 in, and
- 1 kg = 2.20462 lb.

4.3. Interim Analyses

None are planned.

4.4. Subject Disposition

Subject disposition will be tabulated based on the screened population and will include the number screened subjects, randomised subjects, screened failures and subjects re-screened and randomised. If subject is re-screened, such subject will be calculated only once in the screened population. The reason for screen failure will be provided. All screen failure reasons including reasons if subject was re-screened, will be summarized.

In addition, the number of subjects randomised, treated, started treatment after and not on the randomisation date, randomised not-treated, who received a different treatment that they were randomised to, who discontinued treatment, discontinued study, discontinued treatment but completed study along with the reason for treatment discontinuation and the reason for study discontinuation will be provided based on All Randomised Set. The number of subjects in each population with reason for exclusion will be provided based on All Randomised population.

A by-subject listing of study withdrawal/completion information, including the reason for premature study withdrawal, if applicable, will be presented.

Protocol deviations will be listed.

In addition, Kaplan-Meier (KM) curves for time to discontinuation, censoring at last visit (see section 4.2.13), will be plotted by treatment group for the FAS.

4.5. Demographic and Baseline Characteristics

Demographic and baseline characteristics and medical history will be summarized for the FAS, PP, and SAF sets by treatment group using descriptive statistics. No formal statistical comparisons will be performed. All demographic and baseline characteristics will be provided in data listings.

4.5.1. Demographics

Demographics will include country, region (Latin America [Argentina, Brazil], Europe [Croatia, Georgia, Germany, Italy, Netherlands, Poland, Switzerland, United Kingdom, Romania, Spain, Sweden, Ukraine], Rest of the World [Israel, Lebanon, Singapore]), age at time of randomisation (years), randomisation age category (<18, 18-64, 65-84, >=85 years and <70 years vs. >=70 years), sex, ethnicity (Hispanic or Latino/a or of Spanish origin, not Hispanic or Latino/o or of Spanish origin, not reported, unknown), and race (American Indian or Alaska Native, Asian Indian, Black or African American, Chinese, Filipino, Japanese, Korean, Native Hawaiian or Other Pacific Islander, Other Asian, Vietnamese, White, Other). Additional listing with demographic data for screen failure subjects will be created.

4.5.2. Baseline Disease Characteristics

Baseline disease characteristics will include:

- 1) History of cardiovascular risk factors:
 - any risk factor,
 - smoking,
 - hypertension,
 - dyslipidaemia,
 - diabetes mellitus,
 - atrial fibrillation,
 - myocardial infarction,
 - angina pectoris,
 - stroke,
 - coronary revascularization,
 - chronic kidney disease.
- 2) Index hospitalisation information (screening acute heart failure):
 - aetiology (ischaemic, non-ischaemic, unknown; if non-ischaemic, hypertensive, valvular, idiopathic, congenital, other),
 - AHF duration (newly diagnosed at Index hospitalisation, known documented HF prior to Index hospitalisation),
 - time since initial diagnosis to screening (years) as a continuous variable only for those with known HF prior to Index hospitalisation,
 - acute heart failure in the previous 12 months prior to Index hospitalisation (Yes/No),
 - number of hospitalisations in the 12 months prior to screening (for subjects with at least one previous hospitalisation before screening).
- 3) Symptoms and signs of heart failure at time of Index hospitalisation:
 - dyspnoea on exertion,
 - dyspnoea at rest while sitting,
 - orthopnoea and paroxysmal nocturnal dyspnoea,
 - peripheral oedema,
 - pulmonary congestion (crackles, rales),
 - liver enlargement,
 - presence of a third heart sound (S3 gallop),
 - jugular venous distension,
 - jugular venous measurement (cm).

- 4) Other baseline disease characteristics:
- left ventricular ejection fraction (%), left ventricular ejection fraction as categorical variable (<40%, 40-<50%, >=50%)
 - New York Heart Association Classification (Class I, II, III, IV),
 - baseline weight (kg), height (cm), BMI (kg/m²) and temperature (°C),
 - baseline laboratory data: haemoglobin (g/dL), haemoglobin as categorical variable (<10, 10-14, >14), anaemic/non-anaemic subjects (anaemic: adult males with Hb < 13 g/dL, adult females, non-pregnant with Hb <12), serum ferritin (ng/mL), serum ferritin as categorical variable (<100, 100-<300, >=300 ng/mL), transferrin saturation (%), transferrin saturation as categorical variable (<20%, >=20%), phosphorus (mg/dL), phosphorus as categorical variable (<1, 1-<2, 2-<2.5, 2.5-<4.5, >=4.5), creatinine (mg/dL), Brain natriuretic peptide (BNP) (pg/mL), N-terminal-probrain natriuretic peptide (NTproBNP) (pg/mL).
 - medical history information (Percutaneous coronary intervention [PCI], Coronary artery bypass surgery [CABG], Implantable cardioverter defibrillator [ICD], Cardiac resynchronization therapy [CRT]) based on prior procedures.
- 5) Randomisation factors at the time of randomisation:
- sex, age (<70 years/≥70 years),
 - HF aetiology (ischaemic/non-ischaemic/unknown),
 - HF duration (newly diagnosed at Index hospitalisation/known documented HF prior to Index hospitalisation),
 - country.

Note: these will be summarised based on the randomisation file and not based on eCRF data that could have been updated after the randomisation by minimisation.

4.5.3. Medical History

Medical history will be coded using MedDRA and summarized by SOC and PT, presenting numbers and percentages of subjects with each reported history. Medical history will also be listed.

4.5.4. Prior Medications

See section 4.8.8.

4.5.5. Prior Procedures

See section 4.8.9.

4.6. Efficacy Evaluation

The analysis of the primary, secondary and other outcomes described below will be performed on the FAS. Sensitivity analyses will be performed on the PP analysis set.

Due to the Covid-19 pandemic, a sensitivity analyses will be performed for the primary and secondary endpoints on the FAS censoring subjects at index date. The index date is given for each country in the table below and corresponds with the first reported Covid-19 patient in the country. All events after the index date will be excluded and subject's follow-up time will be considered only up to the index date.

Table 4 Index Dates

Country	Index Date
Argentina	02-Mar-2020
Brazil	24-Feb-2020
Croatia	24-Feb-2020
Georgia	25-Feb-2020
Israel	20-Feb-2020
Italy	29-Jan-2020
Lebanon	20-Feb-2020
Netherlands	26-Feb-2020
Poland	03-Mar-2020
Romania	25-Feb-2020
Singapore	22-Jan-2020
Spain	30-Jan-2020
Sweden ¹	NA
United Kingdom ¹	NA
Ukraine	02-Mar-2020

¹ No active subject after the index date in this country.

All inpatient hospitalisations, all urgent heart failure visits, and all deaths will be reviewed by the Clinical Endpoint Committee (CEC) to determine whether they are CV-related or not. CV hospitalisations and urgent heart failure visits will be further adjudicated as due to worsening HF, myocardial infarction, unstable angina, and other CV event.

A death with a cause classified by the adjudication committee as “unknown” will be considered as a cardiovascular death. A death with a cause classified by the adjudication committee as “undetermined” will be considered as a non-cardiovascular death. For all other cases, the final adjudicated classification will be taken into consideration for the analyses described below.

Incomplete hospitalisation dates will be imputed in the following way:

Hospitalisation start date:

1. If the start date of a hospitalisation is partially missing and the month and year or the year are equal to those of the randomisation date and the hospitalisation end date is after or equal to the randomisation date or missing, then the hospitalisation start date will be imputed as the randomisation date.
2. If the hospitalisation end date is before the randomisation date, the hospitalisation start date will be imputed as the hospitalisation end date if the month and/or year is the same.
3. If the start date is completely missing, then the start date will be imputed as the hospitalisation end date.
4. Otherwise the month and/or day will be replaced by January and/or 1.

Hospitalisation end date:

1. Incomplete stop dates will be imputed as the last day of the month/year if day/month is missing, or the date of death, whichever is earlier. If imputed end date is after End of Study (see section 4.2.13), End of Study date will be imputed as stop date instead.
2. In all other cases the incomplete stop date will not be imputed.

For all analyses up to 375 days, study day 375 is included. Similarly, for analyses up to day 30, study day 30 is included.

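### The hospitalisation date rules can turn a short readmission with no recorded month into a stay of hundreds of days starting at or near randomisation, and can end a late stay before it begins

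*SAP*

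**What the plan says.** SAP 4.6 (Efficacy Evaluation) lists the rules for incomplete hospitalisation dates.

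- **Partial start matching randomisation.** This covers records where "the start date of a hospitalisation is partially missing and the month and year or the year are equal to those of the randomisation date" with an end date that is missing or not before randomisation; "then the hospitalisation start date will be imputed as the randomisation date".
- **Other partial starts.** If the end date precedes randomisation, the start takes the end date. In the remaining cases, "Otherwise the month and/or day will be replaced by January and/or 1".
- **Fully missing start.** "If the start date is completely missing, then the start date will be imputed as the hospitalisation end date".
- **Partial end.** The end moves to the close of the recorded month or year, or to death when that came first. If the result falls after End of Study, "End of Study date will be imputed as stop date instead".
- **Any other incomplete end.** "In all other cases the incomplete stop date will not be imputed".

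SAP 4.2.13 supplies the cap: "End of study is defined as the date of the Week 52 visit for subjects completing the study". For everyone else it is the early-termination visit.

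In the partial-start rules, a known end date only decides whether the stay fell before or after randomisation. It does not limit the length of the imputed stay, and no rule refers to index discharge.

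These dates feed several analyses. SAP 4.6.2 takes time to first event from the admission date, decides 30-day membership by that date, and counts days lost from both dates. SAP 4.6.1 uses the admission date in the joint frailty model.

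**The concern.** Subjects are randomised and first dosed as inpatients (Protocol 4.1.2), so the randomisation date is about the least plausible date for a readmission. SAP 4.6.1 and 4.6.2 also place prolonged index hospitalisations on the randomisation date. A readmission moved there by imputation cannot be told apart from one of those.

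The rule closely parallels the adverse-event rule in SAP 4.8.2, which sends a partial onset to first dose. That is cautious when the only question is whether an event is treatment-emergent. It does not suit a date that fixes a duration or decides entry to a 30-day window.

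The End of Study cap conflicts with the follow-up plan. Protocol 5.4.2 keeps following subjects who stop visits for hospitalisation and survival, unless they withdraw consent. SAP 4.6.1 and 4.6.2 count events to the last known date or study day 375. A stay after early termination is therefore in scope, but its imputed end can be set before it began.

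At stake are days lost, which is one of the five secondary endpoints under Hochberg's procedure; time to first event, one form of which is also in that family; the joint frailty model; the 30-day endpoints; and the Covid-19 sensitivity analysis.

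**Working it through.** The plan gives no figure for these rules, so there is none to reproduce. The check applies them literally, with study day = date − randomisation date + 1 and inclusive stay = end − start + 1. All dates below are illustrative.

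**Month and day missing, same year as randomisation.** Randomised 4 March 2019 (day 63 of the year), admission recorded as 2019, discharged 20 November 2019 (day 324). The start becomes 4 March, which is Day 1. Stay = 324 − 63 + 1 = 262 days.

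**Month and day missing, following year.** Randomised in December 2018, same recorded admission and discharge. The start becomes 1 January 2019. Stay = 324 − 1 + 1 = 324 days. For randomisation on 20 December the start is Day 13. It falls within 30 days for any randomisation from 3 December onwards (Day 30).

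If the true stay was 10 days (assumption), the excess is 262 − 10 = 252 or 324 − 10 = 314 days.

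**Only the day missing.** The start moves to the first of the recorded month, or to randomisation if that is in the same month. The largest shift is from the 31st to the 1st, 30 days. A true stay of 20–28 November (9 days) becomes 1–28 November (28 days).

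**How often the rules distort an affected record.** The rules were applied to 200,000 hypothetical readmissions. The assumptions, none of them from the documents, were randomisation uniform over 2018, true start uniform on Days 5–365, a true stay of 9 days and a known end date.

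| Start recorded as | On Day 1 | Within 30 days (true 7%) | Mean stay | Longest stay |
|---|---|---|---|---|
| Year only | 50% | 57% | 131 days | 373 days |
| Month and year | 3.4% | 11% | 23 days | 39 days |

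**End of Study cap.** Randomised 4 March 2019, early-termination visit 1 June 2019 (Day 90), still followed, admitted 10 August 2019 (Day 160), end recorded as August 2019. The end is imputed as 31 August, which is after 1 June, so it is reset to 1 June. Stay = 90 − 160 + 1 = −69 days.

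**Covid-19 analysis.** A year-only 2020 admission in a subject randomised in 2019 becomes 1 January 2020. The earliest index date in SAP Table 4 is 22 January 2020, so an event after the index date can be kept as if it came before.

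**Scale against the endpoint, per arm of 550.** The sample-size section gives 2 × (35 − 6) = 58 HF hospitalisations and 12 CV deaths per 100 subjects.

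- Hospital days: 5.5 × 58 = 319 stays; at an assumed 10 days each, 3,190 days.
- Death days: 5.5 × 12 = 66 deaths. If spread evenly and counted to Day 375 (assumption), 66 × 187.5 = 12,375 days.
- One bad record: 252/3,190 = 7.9% to 314/3,190 = 9.8% of hospital days, but 252/15,565 = 1.6% to 314/15,565 = 2.0% of all days lost.

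**The case against.** The strongest reply is that the trigger should be rare. Protocol 10.3.1 requires hospitalisation and discharge dates in the eCRF, Protocol 9.2.3.14 asks sites for discharge letters for adjudication, and incomplete entries are queried. A committee-confirmed HF stay with an exact discharge date but only a year of admission should be unusual. That stands: the documents do not say how often dates are incomplete, and few records are expected. CV death also gives days lost many large values already, so one bad record is diluted, as the last calculation shows.

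A reader might infer more than the documents support in four respects:

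- **That any partial date produces a very long stay.** It takes a missing month as well as a missing day.
- **That a Day-1 readmission is impossible.** Protocol 4.1.2 lets a subject go home on the day of randomisation after 30 minutes of observation. Such a readmission is implausible, not impossible.
- **That a stay with no end date is lost from the count.** SAP 4.6.2 counts days lost up to the last known date or Day 375, which can be read as truncating an open stay there. The date rules leave the end blank. This is an ambiguity, not a stated omission.
- **That the primary result is at risk or biased.** The primary negative binomial model in SAP 4.6.1 uses event counts with a follow-up offset. Moving a start within follow-up leaves the count unchanged, apart from edge cases at Day 375 and the rule merging a same-day admission and death. The rules are the same in both arms, and no direction of bias is shown.

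**Conclusion.** The concern holds within those limits. As written, the rules give wrong durations and wrong 30-day status when the admission month is missing, and can give a negative stay after early termination. The distortion is about 250–315 days for a worst-case year-only record (assuming a true stay of about 10 days) and at most 30 days when only the day is missing. On the planning figures, one year-only record adds about 2% to an arm's total days lost. That rests on the assumed 10-day stay and the assumed counting of death days.

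The exposed analyses are days lost, time to first event, the joint frailty model, the 30-day endpoints and the Covid-19 sensitivity analysis. Few affected records are expected, but the rules should be corrected because the change is cheap and one of the endpoints is alpha-controlled.

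**What to change.** Amend SAP 4.6 as follows.

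1. **Partial starts, readmissions only.** Prolonged index stays keep the randomisation date. The lower bound is the later of the day after index discharge and the first day compatible with the recorded month or year. The upper bound is the earlier of the end date and the last compatible day. SAP listing 16.2.2.2 already carries admission and discharge dates for all randomised subjects.
2. **Month missing, end date known.** Use the end date minus the pooled blinded median HF stay, kept within those bounds. In the first example, with an assumed median of 10 days counted inclusively, the start becomes 11 November 2019 (Day 253) instead of Day 1.
3. **End dates.** Replace the End of Study cap by the earliest of death, last known date and Day 375, and never let an end precede its start.
4. **No end date.** Count to that cap only if the stay is recorded as ongoing. If the patient was discharged on an unknown date, use start plus the pooled blinded median stay, capped in the same way. Running every missing end to the cap would recreate the fault: a Day-30 admission in a subject last seen on Day 365 would become 365 − 30 + 1 = 336 days.
5. **Sensitivity run.** Repeat the 30-day and days-lost endpoints, excluding or varying records with an imputed month. The SAP should also say how a record with neither a month nor an end date is handled.

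The cost is SAP wording and a little derivation code; no new data are needed. The downside is that a median-based imputation understates truly long stays, which the sensitivity run addresses.
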